#### 9.1.3 Lost to follow-up

For subjects whose status is unclear because they fail to appear for study visits without stating an intention to discontinue or withdraw, the investigator must show "due diligence" by documenting in the source documents steps taken to contact the subject, e.g. dates of telephone calls, registered letters, etc. A subject should not be considered as lost to follow-up until due diligence has been completed or until the end of the study.

# 9.1.4 Study stopping rules

The study may be put on hold pending a full safety data review, if one of the following criteria is met:

- 1. Three or more study medication-related serious adverse events (SAE) reported
- 2. The Sponsor considers that the number and/or severity of AEs, abnormal safety monitoring tests or abnormal laboratory findings justify putting the study on hold.

The study may resume following the safety review if Lead Investigator(s) and sponsor agree it is safe to proceed.

Any restart following a temporary hold due to stopping rules being met will require the Competent Authorities and Ethic Committees approve the study to proceed, as required per country regulations.

# 9.1.5 Early study termination by the sponsor

The study can be terminated by Novartis at any time for any reason. This may include reasons related to the benefit/risk assessment of participating in the study, practical reasons (including slow enrollment), or for regulatory or medical reasons. In taking the decision to terminate, Novartis will always consider the subject welfare and safety. Should early termination be necessary, subjects must be seen as soon as possible and treated as a prematurely withdrawn subject and undergo all assessments of the premature withdrawal visit. The Investigator should ensure contact is made as quickly as possible by telephone and/or e-mail and/or letter. If the study is stopped for a change in the benefit/risk assessment or for medical reasons, patients may be instructed to stop taking the investigational drug QBW251 immediately. Else, patients may be instructed to continue QBW251 intake until they can return to the site for a final assessment. The investigator may be informed of additional procedures to be followed in order to ensure that adequate consideration is given to the protection of the subject's interests. The investigator or sponsor depending on the local regulation will be responsible for informing IRBs/IECs of the early termination of the trial.

# 9.2 Study completion and post-study treatment

Study completion is defined as when the last subject finishes their Study Completion visit and any repeat assessments associated with this visit have been documented and followed-up appropriately by the Investigator or, in the event of an early study termination decision, the date of that decision (e.g. Each subject will be required to complete the study in its entirety and thereafter no further study treatment will be made available to them).

All randomized and/or treated subjects should have a safety follow-up call conducted 30 days after last administration of study treatment. The information collected is kept as source documentation. All SAEs reported during this time period must be reported as described in Section 10.1.3 and SOM. Documentation of attempts to contact the subject should be recorded in the source documentation.

# 10 Safety monitoring and reporting

# 10.1 Definition of adverse events and reporting requirements

#### 10.1.1 Adverse events

An adverse event (AE) is any untoward medical occurrence (e.g. any unfavorable and unintended sign [including abnormal laboratory findings], symptom or disease) in a subject or clinical investigation subject after providing written informed consent for participation in the study. Therefore, an AE may or may not be temporally or causally associated with the use of a medicinal (investigational) product.

The investigator has the responsibility for managing the safety of individual subject and identifying adverse events.

Novartis qualified medical personnel will be readily available to advise on trial related medical questions or problems.

The occurrence of adverse events must be sought by non-directive questioning of the subject at each visit during the study. Adverse events also may be detected when they are volunteered by the subject during or between visits or through physical examination findings, laboratory test findings, or other assessments.

Adverse events must be recorded under the signs, symptoms, or diagnosis associated with them, accompanied by the following information (as far as possible) (if the event is serious refer to Section 10.1.2):

- 1. The severity grade:
  - mild: usually transient in nature and generally not interfering with normal activities
  - moderate: sufficiently discomforting to interfere with normal activities
  - severe: prevents normal activities
- 2. Its relationship to the study treatment. If the event is due to lack of efficacy or progression of underlying illness (i.e. progression of the study indication) the assessment of causality will usually be 'Not suspected.' The rationale for this guidance is that the symptoms of a lack of efficacy or progression of underlying illness are not caused by the trial drug, they happen in spite of its administration and/or both lack of efficacy and progression of underlying disease can only be evaluated meaningfully by an analysis of cohorts, not on a single subject
- 3. Its duration (start and end dates) or if the event is ongoing, an outcome of not recovered/not resolved must be reported
- 4. Whether it constitutes a SAE (see Section 10.1.2 for definition of SAE) and which seriousness criteria have been met
- 5. Action taken regarding study treatment. All adverse events must be treated appropriately. Treatment may include one or more of the following:
  - Dose not changed
  - Dose Reduced/increased
  - Drug interrupted/withdrawn

#### 6. Its outcome

- not recovered/not resolved
- recovered/resolved
- recovering/resolving
- recovered/resolved with sequelae
- fatal
- unknown

Conditions that were already present at the time of informed consent should be recorded in medical history of the subject.

Adverse events (including lab abnormalities that constitute AEs) should be described using a diagnosis whenever possible, rather than individual underlying signs and symptoms.

Adverse event monitoring should be continued for at least 30 days following the last dose of study treatment.

Once an adverse event is detected, it must be followed until its resolution or until it is judged to be permanent (e.g. continuing at the end of the study), and assessment must be made at each visit (or more frequently, if necessary) of any changes in severity, the suspected relationship to the interventions required to treat it, and the outcome.

Information about adverse drug reactions for the investigational drug can be found in the Investigator's Brochure (IB).

Abnormal laboratory values or test results constitute adverse events only if they fulfill at least one of the following criteria:

- they induce clinical signs or symptoms
- they are considered clinically significant
- they require therapy

Clinically significant abnormal laboratory values or test results must be identified through a review of values outside of normal ranges/clinically notable ranges, significant changes from baseline or the previous visit, or values which are considered to be non-typical in subjects with the underlying disease. Alert ranges for laboratory and other test abnormalities are included in Appendix 1.

Follow the instructions found in the SOM for data capture methodology regarding AE collection for subjects that fail screening.

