As the completed thorough QT study (CQBW251A2105) indicated that QBW251 at 300 mg b.i.d. did not have clinically relevant effects on studied ECG parameters, single ECGs pre- and post-dose at Tmax will be performed at visits on Day 1, Day 28, Day 56 and Day 84 (end of treatment). These assessments will be complemented by PK sampling (trough and Cmax) on the matching timepoints, at visits on Day 1, Day 28, Day 56 and Day 84.

The morning dose on Day 84 will be the final dose administration for this treatment period. End of treatment assessment, e.g. safety assessment, lung function assessments and PROs will be performed on Day 84.

If spontaneous sputum collection is not possible at Day 84, site needs to reschedule the visit within 3 days after Day 84 and subject must continue to take study medication. If spontaneous sputum collection attempts are still not satisfactory, investigator may take decision to collect sputum sample after induction by the inhalation of saline. Other assessments that have been completed on Day 84 do not need to be repeated.

A second HRCT will be performed at Day 84 after the morning dose of study medication at site. If the HRCT can't be performed at Day 84 for any reason, the assessment needs to be planned within approximately the 3 coming days and patient must continue to take study medication.

In case of symptom deterioration (via e-diary alert), subjects must visit their study center to determine whether exacerbation criteria have been met and an immediate antibiotic treatment may be necessary. In addition, other markers of inflammation such as fibrinogen in blood will be taken to gain more information on systemic inflammation and sputum sample collection to determine if there are changes in pathogen or bacterial load that may have resulted in the exacerbation. Subjects experiencing an exacerbation during the treatment period will continue with the study treatment along with the standard of care (SOC) therapy for an exacerbation (i.e. antibiotics).

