### Safety follow-up call (Day 114)

A follow-up phone call for safety will occur 30 days after the last dose administration. The safety follow-up includes adverse events safety monitoring.

For a complete list of assessments, refer to the Assessment Schedule in Table 8-1.

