### **Risk mitigations:**

Based on the above risk considerations, clinical monitoring will include the use of an electronic diary with the EXACT-PRO questionnaire to enable daily symptoms assessment, as well as safety assessments during visit days at the investigational site. These safety assessments include a careful assessment of adverse events, ECGs, hematologic and blood biochemistry laboratory assessments, urinalysis and vital signs measurements.

As the completed thorough QT study (CQBW251A2105) indicated that QBW251 at 300 mg b.i.d. did not have clinically relevant effects on studied ECG parameters, ECGs pre- and post-dose (at Tmax) will be performed at Day 1 and Day 28 (when steady state exposure is achieved), and at Day 56 and Day 84 (end of treatment). These assessments will be complemented by the corresponding PK sampling (Ctrough and Cmax).

In addition to the sampling described above, additional PK samples are requested to be taken in case of treatment-emergent serious adverse events.

Finally, although serial PK sampling is optional, efforts will be made to have a sub-group of approximately 30 - 40 patients undergo serial PK assessments to further characterize the PK profile of QBW251 in BE patients, which will provide important understanding of the 300 mg b.i.d. dose in BE patients. Women of childbearing potential and sexually active males must be informed that taking the study treatment may involve unknown risks to the fetus if pregnancy were to occur during the study. In order to participate in the study, participants must agree to adhere to the contraception requirements outlined in the exclusion criteria throughout the study and for at least one week following the last administration of investigational medicinal product. If there is any question that the subject will not reliably comply, they should not be entered or continue in the study. Based on the reproductive toxicity studies results, women of childbearing

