# 10.1.3 SAE reporting

To ensure subject safety, every SAE, regardless of causality, occurring after the subject has provided informed consent and until 30 days following the last administration of study treatment must be reported to Novartis safety immediately, without undue delay, but under no circumstances later than within 24 hours of obtaining knowledge of the events (Note: If more stringent, local regulations regarding reporting timelines prevail). Detailed instructions regarding the submission process and requirements are to be found in the investigator folder provided to each site.

- Screen Failures (e.g. a subject who is screened but is not treated or randomized): SAEs occurring after the subject has provided informed consent until the time the subject is deemed a Screen Failure must be reported to Novartis
- Baseline Failures (e.g. A subject who is screened but not randomized/treated after the baseline visit): SAEs collected between time subject signs ICF until time that subject is determined to be a baseline failure.
- Randomized OR Treated Subjects: SAEs collected between time subject signs ICF until 30 days after the subject has discontinued or stopped study treatment.

All follow-up information for the SAE including information on complications, progression of the initial SAE and recurrent episodes must be reported as follow-up to the original episode immediately, without undue delay, and under no circumstances later than 24 hours of the investigator receiving the follow-up information (Note: If more stringent, local regulations regarding reporting timelines prevail). An SAE occurring at a different time interval or otherwise considered completely unrelated to a previously reported one must be reported separately as a new event.

If the SAE is not previously documented in the Investigator's Brochure or Package Insert (new occurrence) and is thought to be related to the study treatment, a CMO & PS Department associate may urgently require further information from the investigator for health authority reporting. Novartis may need to issue an Investigator Notification (IN) to inform all investigators involved in any study with the same study treatment that this SAE has been reported.

Suspected Unexpected Serious Adverse Reactions (SUSARs) will be collected and reported to the competent authorities and relevant ethics committees in accordance with EU Guidance 2011/C 172/01 or as per national regulatory requirements in participating countries.

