Concomitant medications and significant non-drug therapies prior to and after the start of the study treatment will be listed and summarized according to the Anatomical Therapeutic Chemical (ATC) classification system, by treatment group.

Vital signs

Records taken at baseline visit will be considered as baseline value. Otherwise, records take at Day 1 will be considered as baseline value. Vital sign data for all subjects will be listed by treatment group, subject and visit/time, and abnormalities will be flagged. The normal range of vital signs are:

Oral body temperature: 36.5-37.5 °C
Systolic blood pressure: 90-140 mm Hg
Diastolic blood pressure: 50-90 mm Hg

• Pulse rate: 50 - 100 bpmD

ECG evaluations

ECG data will be collected at scheduled visits in single ECG or triplicate ECGs. If triplicate ECGs are performed, then average of the non-missing values of the 3 measurements will be used in the analysis. ECG data will be listed by treatment, subject and visit/time.

For ECGs, a notable QTc value is defined as a QTcF (Fridericia) interval of \geq 450 msec for males or \geq 460 msec for females.

Clinical laboratory evaluations

All laboratory data will be listed by treatment, subject, and visit/time, if normal ranges are available, abnormalities will be flagged. Summary statistics will be provided by treatment and visit/time.

Adverse events

All information obtained on adverse events will be displayed by treatment group and subject.

Summary tables for adverse events (AEs) will summarize only on-treatment events, with a start date during the on-treatment period (treatment-emergent AEs).

The on-treatment period lasts from the date of first administration of study treatment to 1 week after the last actual administration of any study treatment.

The number (and percentage) of subjects with treatment emergent adverse events (events started after the first dose of study medication or events present prior to start of double-blind treatment but increased in severity based on preferred term) will be summarized by treatment, primary system organ class, preferred term and maximum severity.

Separate summaries will be provided for study medication related adverse events, death including on treatment and post treatment (30 days after the last actual administration of study treatment), serious adverse events, other significant adverse events leading to discontinuation.

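### The ±3-day window on the safety follow-up call lets the last scheduled AE/SAE enquiry fall up to 3 days before the 30-day follow-up period ends

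*Protocol*

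**What the plan says.** Several passages set a 30-day period after the last dose.

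- Protocol Section 10.1.1, on AE monitoring: "Adverse event monitoring should be continued for at least 30 days following the last dose of study treatment".
- Protocol Section 10.1.3 covers every SAE, whatever its cause, from consent "until 30 days following the last administration of study treatment must be reported to Novartis safety immediately".
- Protocol Section 12.5.2 and SAP Section 7.2 define the death summary over the same period. The SAP wording is "death including on treatment and post treatment (30 days after the last actual administration of study treatment".

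Two passages time the call from the last dose and give no window. Protocol Section 3.1 says: "A follow-up phone call for safety will occur 30 days after the last dose administration". Section 9.2 says: "All randomized and/or treated subjects should have a safety follow-up call conducted 30 days after last administration of study treatment".

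Table 8-1 gives the safety follow-up column as Day 114 with a tolerance of 3 days either side, that is Day 111 to Day 117. No later contact is scheduled.

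On the last dose, Section 3.1 says: "The morning dose on Day 84 will be the final dose administration for this treatment period". It also provides that, if spontaneous sputum cannot be collected that day, the "site needs to reschedule the visit within 3 days after Day 84 and subject must continue to take study medication". There is similar wording for a delayed HRCT.

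**The concern.** A symmetric window suits a visit with a target date. It does not suit a contact that has to close a period with a stated minimum length. Because the nominal day of the call is the minimum itself, using the minus side for a patient dosed to Day 84 falls short of Section 10.1.1 and departs from Sections 3.1 and 9.2. A site that books calls from Table 8-1 may not notice.

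What is at stake is active enquiry in the last days of the period. Section 10.1.1 relies on non-directive questioning at each contact. After an early call, an SAE or death before day 30 reaches the database only if somebody volunteers it or the site hears of it some other way. The death summary would then describe a 30-day period that was not actively followed to its end in every patient, and the length of follow-up would differ between patients.

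**Working it through.** **Inputs**

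- Planned last dose: Day 84 (Protocol Section 3.1).
- Required period: 30 days after the last dose (Sections 10.1.1 and 10.1.3; death summary in Section 12.5.2 and SAP Section 7.2).
- Call window: Day 111 to Day 117 (Table 8-1).
- Day 84 visit window: Day 81 to Day 87 (Table 8-1). Dosing may continue for up to about 3 days past Day 84 if sputum or HRCT is rescheduled (Section 3.1).

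**Step 1. Reproduce the plan's own figure.** Call day = last-dose day + 30 = 84 + 30 = 114. This matches the nominal Day 114, so the nominal day contains no slack.

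**Step 2. Shortfall for the planned last dose.** Shortfall = (last-dose day + 30) − call day, or zero if that is negative.

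- Call Day 111: 111 − 84 = 27 days after dose; 114 − 111 = 3 days short; 3/30 = 10%.
- Call Day 112: 28 days after dose; 2 days short.
- Call Day 113: 29 days after dose; 1 day short.
- Call Day 114 or later: no shortfall.

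**Step 3. Other last-dose days, with the window held to the study day.**

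| Last dose | Period closes | Call Day 111 | Call Day 114 | Call Day 117 |
|---|---|---|---|---|
| Day 81 | Day 111 | 0 short | 0 short | 0 short |
| Day 84 | Day 114 | 3 short (10%) | 0 short | 0 short |
| Day 87 | Day 117 | 6 short (20%) | 3 short (10%) | 0 short |

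**Step 4. Window counted from the actual last dose, as Sections 3.1 and 9.2 imply.** The call then falls 30 − 3 = 27 to 30 + 3 = 33 days after the dose. The largest shortfall is 3 days whatever the last-dose day.

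**Step 5. After the change.** If the call is made no earlier than 30 days after the actual last dose, the shortfall is zero. The earliest compliant call is Day 114 for a Day 84 last dose and 87 + 30 = Day 117 for a Day 87 last dose. Both lie inside the current window.

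**The case against.** The strongest reply is that the text already sets the rule. Sections 3.1 and 9.2 tie the call to the last dose, and Section 9.2 covers everyone randomized or treated, including patients who stop early, for whom Day 114 has no special meaning. Day 114 is then only the nominal date for a Day 84 last dose. The introduction to Section 8 also asks sites to keep to the designated day as closely as possible. This stands in part: the defect is a conflict between table and text, not a deliberate rule that follow-up may end early. It does not remove the point, because a minus tolerance of 3 days counted from the last dose still gives 27 days.

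Three stronger readings are tempting and are not supported.

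- **That the gap is 6 days.** This needs dosing to run to Day 87, a window fixed to the study day contrary to Sections 3.1 and 9.2, and a call on the earliest permitted day.
- **That an early call lets a site close safety follow-up.** The SAE reporting duty in Section 10.1.3 does not depend on the call. Events within 30 days remain reportable when the site learns of them, and suspected related SAEs remain reportable after that.
- **That the end-of-study visit (Day 91 ±3) has the same fault.** Section 3.1 says only that it takes place about a week after treatment is completed, and nothing requires it at 7 days or later. The one-week periods elsewhere are an analysis window (Section 12.5.2, SAP Section 7.2) and a participant's contraception duty (Section 4.5: "for at least one week following the last administration of investigational medicinal product"). Neither schedules a visit.

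**Conclusion.** The inconsistency is real and small. For the planned Day 84 last dose, Table 8-1 permits the final scheduled enquiry 1 to 3 days before the 30-day period closes, at most 10% of it. The passages must be reconciled.

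The items exposed are the completeness of SAE collection and of the 30-day death summary. Treatment-emergent AE tables stop one week after the last dose and are unaffected. What is lost is scheduled questioning, not the duty to report, so late events may be missed but need not be. The documents give no rate of late SAEs or deaths and no distribution of call dates, so the expected number missed cannot be calculated.

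The 3-day maximum assumes either a last dose on Day 84 or a window that moves with the last dose. A last dose on Day 81 leaves no shortfall even with a Day 111 call. The SAP records that the study was terminated, so for calls already made the remaining question is how long each patient was in fact followed.

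**What to change.** In Table 8-1, add a footnote to the safety follow-up column: the call is counted from the actual last dose and is made no earlier than 30 days after it, for example with a tolerance of plus 3 days only. Check that Sections 3.1, 9.2, 10.1.1 and 10.1.3 read the same way. Counting from the actual dose also leaves room when dosing runs on: a Day 87 last dose would give Day 117 to Day 120, whereas only Day 117 of the present window reaches 30 days.

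Where calls have already been made, report the actual number of days from last dose to call by treatment group alongside the death summary in SAP Section 7.2, with the number of patients below 30 days.

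The cost is one footnote and, for the terminated study, one short summary. Calls that would have used the minus side move up to 3 days later, or up to 6 in the extended-dosing case. No visit or procedure is added.
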